10.1 Population Flags

Population flags will be finalized and authorized by the Study Statistician and Sponsor during data review meeting prior to database lock as per definitions provided in Section 9. These flags will be included in the analysis datasets.

10.2 Treatment groups

Subjects from ADVM-043-01 study will be enrolled into this follow-up study and the summaries will be created based on the same cohorts as ADVM-043-01 study.

All analyses will be summarized by cohort. The following cohorts will be defined in the analysis datasets. All doses in numeric format will also be included as core variable.

- Cohort 1 (8×10^{13} vg)
- Cohort 2 (4×10^{14} vg)
- Cohort 3 (1.2×10^{15} vg)

10.3 Visits

All analysis datasets with measurements taken at more than one visit will have analysis visit as defined below.

- Screening
- Year 1
- Year 2
- Year 3 (EOS)
- Early Termination

The Screening Assessment should be completed on the same day as the End-of-Study Visit in the prior ADVM-043-01 treatment study.

10.4 Protocol Deviations

A significant deviation is defined as a protocol deviation that affects primary assessments, the safety of a subject or the scientific value of the trial ([REDACTED] [REDACTED]). Significant deviations can include non-adherence to entry criteria; enrollment of the subject without prior Sponsor approval; or non-adherence to FDA regulations or ICH GCP guidelines. Protocol deviations will be reviewed prior to database lock to determine if significant, and all significant deviations will be flagged by the Clinical Trial Manager (CTM) and the Medical Monitoring (MM) team.

Any difference in the deviations classification will be discussed and finalized before the database lock. The protocol deviation summaries will be presented accordingly.

Deviation codes:

Deviations will be coded by the Clinical Trial Manager (CTM) and the Medical Monitoring (MM) team as below.

- Inclusion
- Exclusion
- Assessment – safety
- Visit window
- Informed consent
- Other

10.5 Study Duration

Study Duration (years) = ((Date of Last Visit – Date of Informed Consent) + 1)/365.25.

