4.3 Subject Withdrawal

A subject may withdraw from the study at any time and for any reason without prejudice to their future medical care by the Investigator or at the clinical study site.

Withdrawal from the study will occur under the following circumstances:

- Death
- Withdrawal of consent
- Lost to follow-up
- Study termination by Sponsor

If a subject is lost to follow-up, a minimum of two attempts should be made by the study site personnel to contact the subject. Appropriate contact includes 2 documented phone calls followed by a registered letter before a subject may be listed as lost to follow-up. The measures taken for follow-up and reason for premature study discontinuation should be documented in source documents and CRF.

When a subject withdraws from the study, the reason(s) for withdrawal are to be recorded on the CRF. Whenever possible, all subjects who withdraw from the study are to be encouraged to undergo the End-of-Study assessments at the time of withdrawal.

Sites should obtain follow-up data on any subject who withdraws from the study and has ongoing AEs of interest or SAEs related to ADVM-043. In every case, efforts must be made to undertake protocol-specified safety follow-up procedures.

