4.5 Treatment Allocation

Not Applicable.

5 Assessment Schedule

Subjects will be assessed for up to 3 years post-treatment with ADVM-043. The duration of this long-term follow-up period is 2 years.

Assessment ^a	Post-Treatment Assessment Timepoints			
	Screening ^b	Year 1	Year 2	Year 3 (EOS) ^c
ICF	X			
Inclusion/ Exclusion Criteria	X			
Review and record exposure to other investigational therapies	X	X	X	X
Record AEs of interest/related SAEs	X	X	X	X
Record conmeds ^d	X	X	X	X

Abbreviations: AE = adverse event; conmed = Concomitant medication; EOS = End-of-Study visit; ICF = Informed Consent Form; SAE = serious adverse event; [X] = optional.

^a Assessments may be conducted in the clinic or with a phone call by site personnel.

^b The Screening Assessment should be completed on the same day as the End-of-Study Visit in the prior ADVM-043 treatment study.

^c End-of-Study (EOS) Assessment is scheduled at 3 years post-treatment [REDACTED]; or within [REDACTED] after subject withdrawal.

^d Only concomitant medications for A1AT deficiency (i.e., augmentation therapy), known mutagenic medications / agents, and medications to treat AEs of interest and SAEs related to ADVM-043 should be recorded.

6 Interim Analysis

No interim analysis planned for this study.

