10.6 Adverse Events Flags

An AE is any untoward medical occurrence in an enrolled subject, regardless of its causal relationship to the investigational medicinal product.

Only AEs of interest will be collected and reported in the current study. AEs of interest that are continuing from the previous study will be imported for long term follow-up.

AEs of interest include:

- new malignancy
- new incidence or exacerbation of a pre-existing neurologic disorder
- new incidence or exacerbation of a prior rheumatologic or other autoimmune disorder
- unexpected hospitalization

Study Period:

All AEs will be counted once under the below period in which the AE has started.

- Previous Study: Reported from AE (External).
- Screening – Year 1: If AE start date is after screening and on or before Year 1 visit date.
- Year 1 – Year 2: If AE start date is after Year 1 and on or before Year 2 visit date.
- Year 2 – Year 3 (EOS): If AE start date is after Year 2 and on or before Year 3 visit date.

Related Adverse Events:

- AE (External): includes Possibly, Probably and Definitely Related Adverse Events
- AE: includes Definitely and Likely Related Adverse Events.

Relationship to ADVM-043 will be flagged separately.

Severity:

Subjects with the same AE of interest and different severities will be flagged for the most intense severity. i.e., If the same event has been reported twice with severity 'Grade 1 – Mild' and 'Grade 3 – Severe' then the subject will be flagged as 'Grade 3 – Severe'. AEs that are missing severity will be presented in summary tables as 'Grade 3 – Severe'.

Duration of AEs:

Duration of Adverse events (days) will be calculated as follows: (AE End date – AE Start date) + 1.

For adverse events that are ongoing at end of study, date of end of study will be considered as AE End date.

11 Statistical Analyses

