11.2 Visit Attendance

Number and percentage of subjects who attended each visit (Screening, Year 1, Year 2, and Year 3 (EOS)) will be summarized by cohort. Percentages will be based on FAS Population.

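### SAP 10.5 ends study duration at the last visit and so drops up to about a year for a between-visit death or an exit with no exit assessment, and SAP 10.6 ends ongoing AEs at a date that is not defined at subject level

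*SAP*

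**What the plan says.** SAP 10.5 defines "Study Duration (years) = ((Date of Last Visit – Date of Informed Consent) + 1)/365.25". The result is summarised by cohort in the disposition table (SAP 11.1).

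SAP 10.6 defines AE duration: "Duration of Adverse events (days) will be calculated as follows: (AE End date – AE Start date) + 1". For events not yet resolved it adds: "For adverse events that are ongoing at end of study, date of end of study will be considered as AE End date". AE duration is part of the primary endpoint (SAP 7.1) and appears in the AE listing (SAP 11.7.1.1).

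Neither document says what the end-of-study date is for an individual subject. Protocol 13.0 describes completion of the study as a whole. The abbreviation EOS is expanded as the End-of-Study visit.

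On exits, Protocol 4.3 opens its list with "Withdrawal from the study will occur under the following circumstances" and names death, withdrawal of consent, loss to follow-up and termination by the sponsor. It asks that withdrawing subjects be encouraged, where possible, to have the End-of-Study assessments. SAP 10.3 includes an "Early Termination" analysis visit. The schedule in SAP Section 5 says "End-of-Study (EOS) Assessment is scheduled at 3 years post-treatment", or within a redacted interval after withdrawal, and allows assessments by telephone.

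**The concern.** The two sections use differently worded end dates, and nothing links them. Scheduled contacts are about a year apart, so the choice of end date matters for anyone who stops between them.

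Death is the clear case. No exit assessment is possible, yet the date is normally known, and Protocol 6.10 plans for an autopsy request. SAP 10.5 nevertheless returns the subject's duration to the last yearly visit, so the death lies outside the period in which the subject is reported as followed. The same happens to a subject who leaves and has no exit assessment, although the site may have had later contact. Protocol 4.3 asks sites to obtain follow-up data on withdrawn subjects with ongoing AEs of interest or related SAEs, and Protocol 6.8 has related SAEs reported within 24 hours of awareness.

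The study's only objective is long-term safety, so length of follow-up by cohort is a number that readers will use. This rule can only shorten it, and only for some early exits. Separately, with no subject-level end-of-study date, two programmers could derive different durations for the same ongoing AE.

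**Working it through.** **Inputs.** The formulas are those of SAP 10.5 and 10.6 quoted above. Planned follow-up is from SAP Section 5: "The duration of this long-term follow-up period is 2 years". The visits are those of SAP 11.2: "Number and percentage of subjects who attended each visit (Screening, Year 1, Year 2, and Year 3 (EOS)) will be summarized by cohort".

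**Assumptions.** Consent and Screening fall on the Year 1 date. Year 2 is 366 days after Year 1, and Year 3 is 365 days after Year 2. Visit windows are redacted, so none are applied. No yearly visit is missed.

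**1. The plan's own figure.** For a completer, the last visit is 366 + 365 = 731 days after consent. Study duration = (731 + 1)/365.25 = 2.004 years, which matches the stated 2 years.

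**2. Exit k days after Year 2, no exit assessment.** SAP 10.5 gives (366 + 1)/365.25 = 1.005 years whatever k is. Duration to exit is (366 + k + 1)/365.25.

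| k (days) | SAP 10.5 (years) | To exit (years) | Lost (years) | Lost (%) |
|---|---|---|---|---|
| 1 | 1.005 | 368/365.25 = 1.008 | 0.003 | 1/368 = 0.3 |
| 183 | 1.005 | 550/365.25 = 1.506 | 0.501 | 183/550 = 33.3 |
| 364 | 1.005 | 731/365.25 = 2.001 | 0.997 | 364/731 = 49.8 |

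In whole months, with entry at month 12 and last visit at month 24, exits at months 25, 30 and 35 lose 1/13 = 7.7%, 6/18 = 33.3% and 11/23 = 47.8%.

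A death at k = 183 falls on day 550 counted from consent, while the derived study duration ends on day 367.

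**3. Exit 183 days after Year 1, no exit assessment.** SAP 10.5 gives (0 + 1)/365.25 = 0.003 years. Duration to exit is (183 + 1)/365.25 = 0.504 years.

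**4. The same exit with an assessment on the exit date.** The last visit is now the exit date, so SAP 10.5 gives 184/365.25 = 0.504 years. The loss is zero.

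**5. An AE that starts on the Year 1 date and is ongoing at the exit in step 3.** Study duration is 1 day throughout. AE duration depends on the reading of the end-of-study date:

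- Subject's own last visit: 0 + 1 = 1 day, in agreement with SAP 10.5.
- Subject's exit or death: 183 + 1 = 184 days.
- Scheduled Year 3 date: 731 + 1 = 732 days, which runs past the exit.
- Study-wide completion as in Protocol 13.0: depends on the other subjects, so no figure can be given.

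**The case against.** The strongest reply is that there may be no conflict. SAP 10.6 sets an end date for ongoing AEs and does not say when follow-up ends. Both documents use EOS for a visit. If the end-of-study date means the subject's own Year 3 (EOS) or Early Termination assessment, it coincides with the last visit and the two sections agree. This stands as a possible reading, but the SAP does not state it, and it gives no date for a subject who never has that assessment.

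A reader might infer that everyone who leaves early loses time. The documents do not support that. SAP 10.3 has an Early Termination visit, the schedule calls for an EOS assessment after withdrawal, and a telephone call is enough. Where that assessment takes place, nothing is lost. Deaths between visits remain, as do leavers who are not assessed at exit.

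A reader might also infer that event rates will be overstated. No person-time or exposure-adjusted rate is planned. AE summaries are numbers and percentages of the FAS, and SAP 10.5 does not enter them. Nor is study duration the only guide to length of follow-up, since attendance at each visit and completion with reasons are also summarised by cohort.

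It is also fair that AEs of interest are elicited by questioning at assessments (Protocol 6.6), so time after the last contact is not fully observed for non-fatal events. For subjects lost to follow-up, the last visit will often be the right end date. This argues for using last contact with known status, not the withdrawal date, when there is no exit assessment. It does not justify disregarding a known date of death.

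**Conclusion.** The point holds, at minor severity. Without an exit assessment, SAP 10.5 understates follow-up by 0.003 to 0.997 years for an exit 1 to 364 days after a yearly visit, assuming annual spacing and no missed visit. For a between-visit death this always happens, and the fatal event can then lie outside the reported study duration. The undefined end-of-study date in SAP 10.6 leaves the duration of an ongoing AE open; in the example it is 1, 184 or 732 days on the three readings that can be computed.

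The effect is confined to the study-duration summary and the listed AE durations. The figures are for single illustrative subjects. The SAP gives no sample size and no expected number of early exits, so no cohort-level effect can be derived.

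Two stronger conclusions are not supported. The SAP does not set two contradictory ends of follow-up; it has one explicit rule and one undefined term. And an AE longer than study duration is not in itself a sign of this problem: AEs imported from the previous study start before consent and can exceed study duration whatever end date is used.

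**What to change.** Define one subject-level end-of-study date in the SAP:

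- the date of the Year 3 (EOS) or Early Termination assessment, where one takes place;
- the date of death, if the subject dies;
- otherwise the date of last contact with known status, including for subjects who withdraw without an exit assessment or are lost to follow-up.

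Use this date in place of the last-visit date in SAP 10.5, and name it as the end date for ongoing AEs in SAP 10.6.

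The cost is a few lines of SAP text and one derivation. Protocol 4.3 already requires the reason for withdrawal on the CRF, so at most one date field is added. Results for completers and for subjects assessed at exit do not change. Imported AEs will still be able to exceed study duration, and a footnote to the AE listing can say so.

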10.6 Adverse Events Flags

An AE is any untoward medical occurrence in an enrolled subject, regardless of its causal relationship to the investigational medicinal product.

Only AEs of interest will be collected and reported in the current study. AEs of interest that are continuing from the previous study will be imported for long term follow-up.

AEs of interest include:

- new malignancy
- new incidence or exacerbation of a pre-existing neurologic disorder
- new incidence or exacerbation of a prior rheumatologic or other autoimmune disorder
- unexpected hospitalization

Study Period:

All AEs will be counted once under the below period in which the AE has started.

- Previous Study: Reported from AE (External).
- Screening – Year 1: If AE start date is after screening and on or before Year 1 visit date.
- Year 1 – Year 2: If AE start date is after Year 1 and on or before Year 2 visit date.
- Year 2 – Year 3 (EOS): If AE start date is after Year 2 and on or before Year 3 visit date.

Related Adverse Events:

- AE (External): includes Possibly, Probably and Definitely Related Adverse Events
- AE: includes Definitely and Likely Related Adverse Events.

Relationship to ADVM-043 will be flagged separately.

Severity:

Subjects with the same AE of interest and different severities will be flagged for the most intense severity. i.e., If the same event has been reported twice with severity 'Grade 1 – Mild' and 'Grade 3 – Severe' then the subject will be flagged as 'Grade 3 – Severe'. AEs that are missing severity will be presented in summary tables as 'Grade 3 – Severe'.

Duration of AEs:

Duration of Adverse events (days) will be calculated as follows: (AE End date – AE Start date) + 1.

For adverse events that are ongoing at end of study, date of end of study will be considered as AE End date.

11 Statistical Analyses

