1.0 BACKGROUND

A clinical research subject who has been exposed to an investigational gene therapy may be at risk for delayed adverse events because of the vector that delivers the transgene or because of persistent biological activity of the investigational medicinal product. Some adverse events could be delayed by months or years. Therefore, to mitigate those risks, and per the United States Food and Drug Administration recommendations for the long-term follow-up observation of subjects who received gene therapy products, Study ADVM-043-03 is to be conducted in subjects previously treated with ADVM-043 and will follow them for a total of 3 years post treatment.

The advantage of adeno-associated viral (AAV) vectors in gene therapy is the low propensity of vector genome integration in the host DNA. However, recently there has been attention to potential AAV-induced genotoxicity from systemic or liver-directed gene therapy. To date, mouse studies have varied in their findings in neonatal, juvenile, and adult animals.

AAV genome integration has been observed in neonatal mice that demonstrated a higher risk of developing hepatocellular carcinoma after AAV administration (Bell 2005; Chandler 2015). This insertional mutagenesis to an oncogenic locus (Rian) reported after neonatal gene delivery is thought to be influenced by higher transcriptional activity of that locus during the neonatal period of development, as juvenile and adult rodents have not demonstrated similar findings. Furthermore, the site of AAV integration in mice has no analogue in humans (Bell 2005; Chandler 2015). Long-term larger animal studies in dogs (through 8 years) and nonhuman primates (through 5 years) have not shown such genotoxicity (Niemeyer 2009; Nathwani 2011).

To date, there has been no evidence of tumor formation or long-term hepatotoxicity in a hemophilia B gene therapy trial where 10 subjects were treated with systemic AAV. The study demonstrated durable and stable expression of transgenic factor IX at therapeutic levels for at least 4 years after vector delivery (Nathwani 2014).

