3.2 Study Duration

Subjects will be assessed for up to 3 years post-treatment with ADVM-043. The duration of this long-term follow-up period is 2 years.

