15.0 APPENDICES

15.1 Appendix 1 Schedule of Assessments

Assessment ^a	Post-Treatment Assessment Timepoints			
	Screening ^b	Year 1 ^b [REDACTED]	Year 2 [REDACTED]	Year 3 (EOS) ^c [REDACTED]
ICF	X			
Inclusion/ Exclusion Criteria	X			
Review and record exposure to other investigational therapies	X	X	X	X
Record AEs of interest/related SAEs	X	X	X	X
Record conmeds ^d	X	X	X	X

Abbreviations: AE=adverse event; conmed=Concomitant medication; EOS=End-of-Study visit; ICF=Informed Consent Form; SAE=serious adverse event; [X]=optional.

- a Assessments may be conducted in the clinic or with a phone call by site personnel.
- b The Screening Assessment should be completed on the same day as the End-of-Study Visit in the prior ADVM-043 treatment study.
- c End-of-Study (EOS) Assessment is scheduled at 3 years post-treatment [REDACTED], or within [REDACTED] after subject withdrawal.
- d Only concomitant medications for A1AT deficiency (i.e., augmentation therapy), known mutagenic medications / agents, and medications to treat AEs of interest and SAEs related to ADVM-043 should be recorded.

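### SAP 10.6 never derives time from dosing to AE onset, and its visit-based periods leave some events with no period

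*SAP*

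**What the plan says.** The rationale in Protocol 1.0 is late toxicity: "Some adverse events could be delayed by months or years". SAP 10.6 counts each AE a single time, in the study period in which it began, and defines four periods. The first depends on where the record came from: "Previous Study: Reported from AE (External". The other three depend on the start date relative to visit dates. *Screening – Year 1*, for example, applies "If AE start date is after screening and on or before Year 1 visit date", and *Year 1 – Year 2* and *Year 2 – Year 3 (EOS)* follow the same pattern.

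SAP 10.3 also lists Early Termination as an analysis visit, but no period in 10.6 refers to it. From the prior study, 10.6 brings across only those AEs of interest that are still ongoing.

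On timing, Protocol 3.2 says "The duration of this long-term follow-up period is 2 years", and SAP section 5 says "Subjects will be assessed for up to 3 years post-treatment with ADVM-043". Protocol Appendix 1 adds: "The Screening Assessment should be completed on the same day as the End-of-Study Visit in the prior ADVM-043 treatment study". Both schedules mark AE recording at Screening, although Protocol 5.1 lists only consent and entry criteria for that assessment.

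The derived time variables are AE duration (SAP 10.6) and study duration counted from consent (SAP 10.5). Administration data are listed by subject (SAP 11.6).

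**The concern.** For a one-off gene therapy, the natural clock for a delayed event starts at dosing. The SAP holds both dates needed but never subtracts one from the other. It uses visit dates instead, which move with attendance and do not exist for missed visits.

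The period rule also mixes two criteria, data source for the first period and date for the rest. An event can therefore fail all four definitions, although the SAP intends every AE to have one period. The cases are foreseeable. An AE may be recorded at Screening itself, a later telephone contact may bring out an earlier diagnosis, or a subject may leave between annual visits. At stake are the completeness of the onset classification for the study's only endpoint and a reader's ability to see how late events arose.

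**Working it through.** **Inputs from the documents**
- Total follow-up is up to 3 years after dosing: "End-of-Study (EOS) Assessment is scheduled at 3 years post-treatment" (SAP section 5).
- This study lasts 2 years (Protocol 3.2).
- Visit labels count from treatment: the SAP section 5 table is headed "Post-Treatment Assessment Timepoints".
- Screening falls on the day of the prior study's last visit (Protocol Appendix 1), including for subjects who did not complete that study (Protocol 5.1).
- The onset date is collected (Protocol 6.6).

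**Assumptions (not in the documents)**
- A year is 365 days, so Year 2 is day 730 and Year 3 is day 1095.
- A completer of the prior study is screened at day 365. Early leavers are illustrated at days 183 and 91.
- Year 1 may be held 0, 14 or 30 days after a completer's Screening, since the windows are redacted.

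**Step 1: reproduce the stated duration.** Year 3 − Year 1 = 3 − 1 = 2 years, which matches the plan. Entry is then at 3 − 2 = 1 year after dosing.

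**Step 2: apply the four rules to onset days 1 to 1095.** Width of the first in-study period = Year 1 day − Screening day.

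| Subject | Screening day | Year 1 day | Width of *Screening – Year 1* (days) | CRF onset days up to Screening with no period |
|---|---|---|---|---|
| Completer, same day | 365 | 365 | 0 | 365 of 365 |
| Completer, Year 1 14 days later | 365 | 379 | 14 | 365 of 365 |
| Completer, Year 1 30 days later | 365 | 395 | 30 | 365 of 365 |
| Left prior study at about 6 months | 183 | 365 | 182 | 183 of 183 |
| Left prior study at about 3 months | 91 | 365 | 274 | 91 of 91 |

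The last column follows directly from the rules. A record on this study's CRF is not external, so it fails the first definition. The other three all require onset later than Screening.

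**Step 3: withdrawal between visits.** Take Year 1 at day 365, an event at day 500, and no Year 2 or Year 3 visit. *Year 1 – Year 2* needs a Year 2 date, and there is none, so the event has no period. If the withdrawal assessment were treated as the EOS visit, the last period would still need onset after a Year 2 visit that never took place.

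**Step 4: overlap.** No CRF record falls in two periods. No external record with onset on or before Screening falls in more than one.

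**Step 5: time from dosing.** SAP 10.5 starts at consent, the duration in 10.6 starts at AE onset, and 11.6 only lists administration data. None of these gives time from dosing to onset.

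**The case against.** The best defence is that the visits are themselves scheduled by time after treatment, so the periods already give latency in bands of about one year. This stands in part. A reader might infer that an event at month 13 and one at month 35 could not be told apart. If visits run to schedule, the first falls in *Year 1 – Year 2* and the second in *Year 2 – Year 3 (EOS)*. What the bands lack is resolution within a year (months 13 and 23 share a band) and independence from actual visit dates.

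A reader might also infer that events are counted twice at hand-over. The documents do not support that. SAP 10.6 says each AE is counted once, and a CRF re-entry of an imported event would get no period, not a second one. What is missing is a rule linking the external AE data to this study's CRF. That is a data-merge risk to the event count m in SAP section 8. The AE tables in SAP 11.7 count subjects, which a duplicate with the same coding would not change.

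Nor is it established that the first in-study period is empty. The prior study's length is not given and the windows are redacted. Protocol 5.1 treats Screening and enrolment at Year 1 as separate steps, and early leavers give the period real length. On the other side, the protocol's schedule attaches the same-day footnote to Year 1 as well as Screening, while the SAP's copy attaches it to Screening only.

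Finally, latency is not a component of the stated endpoint, and no table in SAP 11.7 is specified by period. The index of tables is redacted, so whether one exists cannot be checked. Onset and dosing dates can both be listed, so latency can be worked out by hand. These points limit the consequence but do not repair the rule.

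**Conclusion.** Two defects hold on the text alone. No time from dosing to onset is derived anywhere. The period rule also leaves two classes of event unassigned: CRF events with onset on or before Screening that are not in the external data, and events after the last scheduled visit attended by a subject who withdraws. The first gap covers every onset day up to Screening, whatever the visit windows are. How many events will fall in either gap cannot be estimated from the documents.

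The near-zero length of *Screening – Year 1* for completers is probable but inferred. It rests on entry at about one year and on Year 1 being held close to Screening. If so, the period would hold mainly subjects who left the prior study early and would not be comparable across subjects.

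The point is moderate. The data are sound and the listings would remain, but a clearly better derivation is available from dates already held, and the SAP should adopt it before database lock.

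**What to change.** In SAP 10.6:
- Derive onset day = AE start date − ADVM-043 administration date + 1.
- Replace the visit-based periods with year 1, 2 or 3 after dosing, assigned from onset day whichever database holds the event. This settles both unassigned cases and removes the dependence on visit dates and on Early Termination.
- Print onset day in the AE listing. Minimum, median and maximum by cohort are optional.
- Footnote the year-1 class as incomplete. Prior-study events that had resolved are not imported, so the row would otherwise understate early events.
- State that an AE found in both the external data and this study's CRF is kept as one linked record, with the prior study's start date and this study's end date and outcome.
- Because SAP 8.1 rules out imputation, provide an unclassified row for start dates too incomplete to place.

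The cost is SAP wording, one derived variable and some cross-database record linkage. No new data collection is needed, provided year 1 is labelled incomplete. Filling that row would require further prior-study AE data.
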